#### **C.6.6.b Classification of Adverse Events**

Monitoring adverse events requires that they be classified as to seriousness, expectedness, and potential relationship to the study drugs, all of which drive the reporting process.

*Seriousness*

A serious adverse event is one that:

- (a) Results in death,
- (b) Is life-threatening (the subject was, in the view of the Principal Investigator, in immediate danger of death from the event as it occurred),
- (c) Requires inpatient hospitalization or prolongation of existing hospitalization,
- (d) Results in persistent or significant disability/incapacity, or
- (e) Is a congenital anomaly/birth defect in the offspring of a participant.

The Common Terminology Criteria for Adverse Events (CTCAE) Version 3.0

(<http://ctep.cancer.gov>) provides a grading system that is used to categorize the severity of adverse events, as follows:

- (a) Grade 1 Mild: transient, requires no special treatment or intervention, does not interfere with daily activities
- (b) Grade 2 Moderate: alleviated with simple treatments, may limit daily activities
- (c) Grade 3 Severe: requires therapeutic intervention and interrupts daily activities
- (d) Grade 4 Life-threatening or disabling
- (e) Grade 5 Death.

A serious adverse event, as defined above, encompasses CTCAE grades 4 and 5, and any Grade 3 event that requires or prolongs hospitalization, or that is disabling.

### *Expectedness*

The purpose of reporting is to provide new, important information on serious reactions or events previously unobserved or undocumented. Therefore, all adverse events will be evaluated as to whether their occurrence was unexpected.

1. Unexpected: An unexpected adverse event or adverse drug reaction is one for which the nature or severity is not consistent with information in the protocol, consent form, or product brochure.
2. Expected: An event is considered expected if it is known to be associated with the study drugs. For this protocol, expected events include the following:
  - a. Bradycardia
  - b. Dizziness

- c. Syncope
- d. Hypotension
- e. Palpitations
- f. Fatigue
- g. Lethargy
- h. Mood changes
- i. Behavior changes
- j. Sleep disturbances
- k. Nightmares
- l. Headache
- m. Nasal congestion
- n. Gastrointestinal pain
- o. Dysgeusia
- p. Nausea
- q. Emesis
- r. Diarrhea
- s. Constipation
- t. Myalgias
- u. Back pain
- v. Peripheral edema
- w. Wheezing
- x. Shortness of breath
- y. Cough
- z. Chest pain
- aa. Renal dysfunction
- bb. Anemia
- cc. Hepatic dysfunction

*Causality*

Causality assessment is required in clinical investigations to help determine which events require expedited reporting. The following criteria will be used to determine causality:

1. Not Related: The event is clearly related to other factors, such as the subject's clinical state, or non-study drugs or interventions.
2. Possibly Related: The event follows a compatible temporal sequence from the time of administration of the study drug, but could have been produced by other factors such as the subject's clinical state or non-study drugs or interventions.
3. Probably Related: The event follows a reasonable temporal sequence from the time of drug administration, and cannot be reasonably explained by other factors such as the subject's clinical state, or non-study drugs or interventions.

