### **B.3.5 Safety Profile of carvedilol**

Carvedilol is a commonly used medication in heart failure. Due to efficacy studies in different populations, cardiologists often use carvedilol in the Fontan population. However, there is a lack of data regarding the safety profile of carvedilol specific to the Fontan population. Adverse events will be recorded. While hepatic and renal dysfunction are rare adverse events (<1%) of carvedilol, they are of severe consequence in the Fontan population. Possible hepatic or renal dysfunction associated with carvedilol in Fontan patients has not been previously described. Therefore a comprehensive metabolic panel will be monitored throughout the study. B-type natriuretic peptide (BNP) is a seromarker of heart failure that is associated with important outcomes in the Fontan population. Therefore, BNP will be measured during the study to assess the effect carvedilol has on serum BNP in Fontan patients.

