#### **C.6.6.d Reporting Procedures (Table 2)**

1. Fatal or life-threatening adverse events are to be reported to the IRB within three working days after knowledge of the event. Those that are unexpected and considered

possibly or probably related to the study drug will be reported, by the PI to the DSMB Chair but no later than 7 calendar days after first knowledge of the event, followed by a complete report within 15 calendar days. All other fatal or life threatening events will be reported to the DSMB within 15 days,

2. All other serious (i.e., non-fatal or not life-threatening) adverse events that are unexpected and considered possibly or probably related to the study drug will be reported to the IRB within 7 days of learning of the event. The PI will report the event to the DSMB within 15 calendar days after first knowledge of the event.

3. All other adverse events not meeting the criteria for expedited reporting will be reported quarterly to the DSMB.

4. The following events do NOT need to be reported:

- Planned hospitalizations for non-cardiovascular surgical, diagnostic, or other procedures.
- Planned cardiac catheterization.
- Social admissions in the setting of foster care or other similar circumstances.
- Otitis media
- Streptococcal pharyngitis
- Allergic rhinitis
- Uncomplicated upper respiratory infections
- Short-term (<36 hours) fever with no other symptoms after immunizations
- Uncomplicated gastroenteritis
- Uncomplicated urinary tract infections
- Hospitalizations or emergency room care for trauma, including broken bones, evaluation after motor vehicle accident, or similar incident.

The site investigator or designee will report all serious adverse events to the IRB according to IRB policies.

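### Serious, drug-related hepatic or renal events go by default to the quarterly DSMB report, because both are listed as expected with no severity limit

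*Combined protocol and SAP*

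**What the plan says.** The expectedness part of C.6.6.b gives its aim first: "The purpose of reporting is to provide new, important information on serious reactions or events previously unobserved or undocumented". It then defines two classes. For the first, "An event is considered expected if it is known to be associated with the study drugs". An unexpected event or reaction, by contrast, "is one for which the nature or severity is not consistent with information in the protocol, consent form, or product brochure". The text continues "For this protocol, expected events include the following", and the lettered entries include "aa. Renal dysfunction" and "cc. Hepatic dysfunction". Neither entry carries a grade.

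C.6.6.d uses this classification to set the DSMB clock:

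- **Item 1, fatal or life-threatening events.** If unexpected and possibly or probably related, the DSMB Chair is told within 7 calendar days, with a complete report by day 15. All other events in this class go to the DSMB within 15 days.
- **Item 2, other serious events.** If unexpected and possibly or probably related, they go to the IRB within 7 days and to the DSMB within 15 calendar days.
- **Item 3, the rest.** "All other adverse events not meeting the criteria for expedited reporting will be reported quarterly to the DSMB". Table 2 has the same three tiers and words the last one as a minimum frequency.

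B.3.5 puts hepatic and renal dysfunction at under 1% for carvedilol in general and regards them as grave for Fontan patients. It adds: "Possible hepatic or renal dysfunction associated with carvedilol in Fontan patients has not been previously described". It gives this as the reason for following the metabolic panel. C.6.6 requires every serious adverse event to reach the IRB within 24 hours and has the DSMB meet every 6 months.

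**The concern.** B.3.5 singles out two events as dangerous in this population and as undocumented there with this drug. C.6.6.b says that reporting exists to bring such information forward. Yet the same section places both events on a flat list, and that list removes a serious related case from the 15-day DSMB route unless it is fatal or life-threatening.

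The DSMB is charged with overseeing the trial's progress and safety, and under C.5.1 it may choose to receive results unblinded. What is at stake is how soon it learns of a case that may be the only one in the trial, while enrolment and crossover continue. The primary analysis is not affected.

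**Working it through.** There is no stated figure to reproduce. The check traces one case through the rules and then sizes the delay and the number of cases.

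**Routing.** Take a hospitalization for hepatic dysfunction, judged possibly related and not life-threatening.

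1. Seriousness (C.6.6.b): hospitalization makes it serious.
2. Expectedness (C.6.6.b): hepatic dysfunction is on the list with no grade, so the default class is expected.
3. C.6.6.d item 1 does not apply, because the case is not fatal or life-threatening.
4. Item 2 does not apply, because it requires an unexpected event.
5. Item 3 and the last row of Table 2 apply: the quarterly report.

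A renal case follows the same path.

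**Delay to the DSMB.**

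- One quarter: 365.25 / 4 = 91.3 days. This is the maximum wait.
- Average wait, if events fall evenly over the quarter: 91.3 / 2 = about 45 days.
- Excess over the 15-day limit: 91.3 − 15 = about 76 days at most; 45 − 15 = about 30 days on average.
- Accrual (30 subjects over about 24 months, Overview): 30 / 24 = 1.25 per month. The excess corresponds to about 1.25 × 2.5 = 3.1 subjects randomized at most, and about 1.25 × 1 = 1.25 on average.

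**Timing against crossover.** Table 5 places the end-of-period panels at weeks 12 and 30, and Period 2 starts at week 19. A case brought to light at week 12 therefore falls 7 × 7 = 49 days before Period 2. A 15-day report arrives before that date. A report at the quarterly maximum of 91 days does not; one at the 45-day average just does.

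**Number of cases.** Assumption: the under-1% figure in B.3.5 is a per-subject risk, here varied from 0.1% to 1%, in 30 subjects.

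| Risk per subject | Expected cases | P(at least 1) | P(2 or more) |
|---|---|---|---|
| 0.1% | 0.03 | 3.0% | 0.04% |
| 0.5% | 0.15 | 14.0% | 1.0% |
| 1% | 0.30 | 26.0% | 3.6% |

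For example, 1 − 0.99^30 = 0.260. If the figure applies to each of the two events separately, the ceiling is 2 × 0.3 = 0.6 cases, still below one. The serious and drug-related subset is smaller again. A signal built from several cases is therefore unlikely, and prompt notice of a single case carries most of the information.

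**Risk lists.** C.6.1 and C.6.2.a name neither hepatic nor renal dysfunction, although C.6.6.b lists both as expected. C.6.6.e asks after each DSMB meeting whether event frequency exceeded what the consent indicated, and C.6.2.a gives no rate for either event.

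**The case against.** The strongest defence is that the listing obeys its own definition. Expectedness is a question about the drug, and B.3.5 itself calls these events rare adverse events of carvedilol. That they are undescribed in Fontan patients is a separate statement, and both can be true. This stands. A reader might infer that the two entries are mistakes to be deleted; the documents do not support that, and deletion would put the list at odds with its definition.

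Second, severity can make an event unexpected, and nothing says that the list overrides this test. This also stands, so the quarterly route is a default and not a certainty. But with no grade on the list and B.3.5 already describing the events as grave, the safeguard rests on individual judgement.

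Third, a reader might infer that such a case escapes prompt independent oversight. It does not: C.6.6 sends all serious adverse events to the IRB within 24 hours, and the end of C.6.6.d also requires all of them to go to the IRB. C.5.4 and C.7.6 let the investigator act for the affected subject without waiting for the DSMB. What remains is that no text requires the IRB or the investigator to tell the DSMB promptly.

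Fourth, the delay is easily overstated. About 90 days is a ceiling, and the extra subjects randomized count as harm only if a single report would halt enrolment, which no rule says.

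**Conclusion.** The point holds as a gap in DSMB notification. By default, a serious, possibly or probably related hepatic or renal case that is not fatal or life-threatening reaches the DSMB after up to about 90 days, about 45 on average, instead of within 15. This sits badly with B.3.5 and with the stated purpose of reporting. The average assumes events spread evenly over the quarter, and the case counts assume that the under-1% figure is a per-subject risk.

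Three stronger readings are not supported:

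- Fatal or life-threatening cases are not left to the quarterly report. They reach the DSMB within 15 days even when expected; the listing changes only the first notice, from 7 days to 15.
- The DSMB cannot be called the one body that sees data by arm. C.5.1 leaves it to choose blinded or unblinded results, and the pharmacy holds the assignments.
- The consent form cannot be said to omit these events. The lists in C.6.1 and C.6.2.a are worded as open lists, and the form itself is not among the documents.

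This is a cheap improvement to safety oversight, with a small expected number of cases.

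**What to change.** Keep both events on the expected list. State in C.6.6.d and Table 2 that any serious, possibly or probably related hepatic or renal event is reported to the DSMB on the timeline for unexpected events, whatever its expectedness. For a case that is neither fatal nor life-threatening, that is 15 calendar days.

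Reconcile the risk lists in C.6.1 and C.6.2.a with the expected list, and check the consent form against both.

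The cost is wording in the protocol and, if the check shows a gap, in the consent form. The added reporting load is fewer than one expedited report over the trial: under 0.01 × 30 = 0.3 cases on the stated assumption.

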#### **C.6.6.c Identification of and Data Collection Procedures for Adverse Events**

In this trial, a primary safety concern as well as one of the secondary end points is to capture and compare adverse drug reactions between carvedilol versus placebo. In addition, following standard clinical trial procedures, information on other adverse events will be collected.

*Adverse drug reactions* will be assessed at baseline, at the end of up-titration, and at each study visit through a standardized questionnaire that will be administered by the study coordinators or investigators. The assessment at baseline will be obtained while the subject is not taking any study drug and is essential to accurate assessment of drug effects. *Adverse events* that are not considered adverse drug reactions will be identified when they are reported to the clinical center or during scheduled study visits by study coordinators and investigators. Subjects and families will be encouraged to report any serious event to study personnel as soon as the event occurs, rather than waiting for scheduled visits.

#### **C.6.6.d Reporting Procedures (Table 2)**

1. Fatal or life-threatening adverse events are to be reported to the IRB within three working days after knowledge of the event. Those that are unexpected and considered

possibly or probably related to the study drug will be reported, by the PI to the DSMB Chair but no later than 7 calendar days after first knowledge of the event, followed by a complete report within 15 calendar days. All other fatal or life threatening events will be reported to the DSMB within 15 days,

2. All other serious (i.e., non-fatal or not life-threatening) adverse events that are unexpected and considered possibly or probably related to the study drug will be reported to the IRB within 7 days of learning of the event. The PI will report the event to the DSMB within 15 calendar days after first knowledge of the event.

3. All other adverse events not meeting the criteria for expedited reporting will be reported quarterly to the DSMB.

4. The following events do NOT need to be reported:

- Planned hospitalizations for non-cardiovascular surgical, diagnostic, or other procedures.
- Planned cardiac catheterization.
- Social admissions in the setting of foster care or other similar circumstances.
- Otitis media
- Streptococcal pharyngitis
- Allergic rhinitis
- Uncomplicated upper respiratory infections
- Short-term (<36 hours) fever with no other symptoms after immunizations
- Uncomplicated gastroenteritis
- Uncomplicated urinary tract infections
- Hospitalizations or emergency room care for trauma, including broken bones, evaluation after motor vehicle accident, or similar incident.

The site investigator or designee will report all serious adverse events to the IRB according to IRB policies.

**Table 2. Reporting of Adverse Events**

Seriousness	Relatedness	Expectedness	Reporting Timeframe
Fatal or life threatening	Related or Unrelated	Expected or Unexpected	Within 3 days of learning of the event
Serious, but not fatal or life threatening	Related	Unexpected	Within 7 days of learning of the event
All other			At least quarterly

**C.6.6.e Reporting Adverse Events to the Institutional Review Board**

After each DSMB meeting, a Summary Report of Adverse Events will be prepared and submitted at the continuing review to the IRB. The Summary Report will contain the following information:

- A statement that a DSMB review of outcome data, adverse events, and information relating to study performance took place on a given date
- A statement as to whether or not the frequency of adverse events exceeded what was expected and indicated in the informed consent
- A statement that a review of recent literature relevant to the research took place
- The DSMB’s recommendation with respect to progress or need for modification of the protocol or informed consent. If the DSMB recommends changes to the protocols or informed consent, the rationale for such changes and any relevant data will be provided
- A statement that if safety concerns are identified, the NHLBI Program Official will communicate these promptly to the investigators.

**C.6.6.f Post-Study Procedures for Adverse Events**

All adverse events unresolved at the time of the subject's termination from the study will be followed by the investigators until the events are resolved, the subject is lost to follow-up, or the adverse event is otherwise explained or has stabilized. At the last scheduled contact, the investigator will instruct each subject or parent/guardian to report any subsequent event(s) occurring in the next 30 days that the subject, parent, or the subject's personal physician believes might reasonably be related to the study drugs.

Any death or other clinically serious adverse event that may be related to the study drugs and that occurs at any time after a subject has discontinued study drug or terminated study participation will be reported.

## C.7 Measurements

C.7.1. Study Data and Measurements are outlined in Table 4 and 5

**Table 4. Screening Measures**

Screening Phase	
	Visit 0 (week -2-0)
Exercise Test	x
Pregnancy Test	x*
BNP, CBC, CMP	x

\*to be performed on females of child bearing age only (12 years of age or older)

**Table 5. Treatment Phase Measures**

Treatment Period 1 (week 0-12)						
	Visit 1 (week 0)	Visit 2 (week 1)	Visit 3 (week 2)	Visit 4 (week 3)	Visit 5** (week 8)	Visit 6 week 12
Duration (hrs)	1-1.5	<1	<1	<1	<1	2
Vital signs	x	x	x	x		x
NYHA HF Classifications	x	x	x	x		x
Adverse Drug Effect	x	x	x	x	x	x
Compliance Check		x	x	x	x	x
Safety Labs (CMP, BNP, CBC)	X					x
Exercise Test	x*					x
Study Drug Medication	X_initiate	X- uptitration 1	X- uptitration 2	X-no change		X-after visit stop study medication***
Washout Period (Week 13-18)						
Treatment Period 2 (week 19-30)						
	Visit 7 (week 19)	Visit 8 (week 20)	Visit 9 (week 21)	Visit 10 (week 22)	Visit 11** (week 26)	Visit 12 (week 30)
Duration (hrs)	2	<1	<1	<1	<1	2
Vital Signs	x	x	x	x		x
NYHA HF Classifications	x	x	x	x		x
Adverse Drug Effect	x	x	x	x	x	x
Compliance Check	x	x	x	x	x	x
Safety Labs (CMP, BNP, CBC)	X					x
Exercise Test	x					x
Study Drug Medication	X-initiate	X- uptitration 1	X- uptitration 2	X-no change		after visit stop study medication***

\*-exercise test from screening phase may be used if visit 1 exercise test if done within 14 days of visit 1,

\*\*-may be phone visit

\*\*\*dose of study medication decreased during weeks 6 and 31 and then stopped

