increased systemic vascular resistance. Systemic vascular resistance is increased in Fontan patients which may adversely affect function of the single ventricle. Therefore, carvedilol may provide more physiologic benefit than other more selective beta blockers.

Potential participants in this study are patients with SV who have undergone Fontan palliation, who are now between the ages of 10 years and 35 years. Participants will initially undergo a screening phase which will include an exercise test to determine if they can adequately perform a maximal exercise test ( $\text{RER} > 1.0$  at maximal exercise) and safety laboratories. Participants who are able to exercise as described and who have acceptable safety laboratories will be randomly assigned to receive either carvedilol or placebo for the first 12 week treatment period. After a 6 week washout period, all participants will cross over to the other treatment arm for 12 weeks. Exercise data will be collected at baseline and at 12, 19, and 30 weeks after randomization. The primary aim of the study is to compare the effect of carvedilol therapy to that of placebo therapy on exercise performance as measured by peak oxygen consumption per kilogram. Secondary endpoints include the following: peak heart rate during exercise, submaximal exercise capacity, ventilatory efficiency of carbon dioxide, and safety profile of carvedilol in Fontan patients. The total sample size target of 30 participants will be recruited over approximately 24 months.

There is a lack of controlled clinical trials that have systematically investigated whether carvedilol will benefit Fontan patients. The results of this study will provide preliminary efficacy data for carvedilol in Fontan patients and inform the design and sample size calculations necessary for a large multicenter trial.

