**C.5.3.2. Down-titration of Study Drug**

During the washout period, after treatment period 2 (Table 5) or if it is necessary for a subject to stop the study drug, the subject should optimally be weaned off the drug as follows. Per manufacturer's guidelines, carvedilol will be down-titrated over one week:

- Day 1: 50% of previous dose
- Day 3-5: 25 % of regular dose
- Day 7-10: Stop drug

In the event of severe clinical instability or inability to take the study drug (i.e., severe vomiting), weaning may need to occur over a shorter period of time, at the discretion of the study physician and care providers. Reinitiation of study drug will be considered

after the PI has consulted with the study participant (or legal guardians) and attending cardiologist.

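### The Table 5 footnote puts the first study-drug decrease in week 6, against the week-12 cell it annotates and other sections; secondarily, C.7.2 leaves the permitted washout gap undefined

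*Combined protocol and SAP*

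**What the plan says.** **Stopping drug.** In the study-drug row of Table 5, the Visit 6 (week 12) and Visit 12 (week 30) cells both say "after visit stop study medication". Both carry the three-asterisk footnote, which reads "dose of study medication decreased during weeks 6 and 31 and then stopped".

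**Taper.** C.5.3.2 gives the occasions for weaning as "During the washout period, after treatment period 2 (Table 5) or if it is necessary for a subject to stop the study drug". The taper takes about a week and ends with "Day 7-10: Stop drug". Table 5 heads the interval between the periods "Washout Period (Week 13-18)".

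**Period lengths.** The Overview has subjects "randomly assigned to receive either carvedilol or placebo for the first 12 week treatment period". It continues: "After a 6 week washout period, all participants will cross over to the other treatment arm for 12 weeks". It places the exercise tests at baseline and at 12, 19 and 30 weeks, counted from randomization.

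**Windows.** C.7.2 allows ±14 days for Visits 6 and 12 and ±7 days for Visit 7. Its stated purpose is to leave time to reach the maximum tolerated dose before the Visit 6 and Visit 12 tests. It names no reference date for the windows.

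**Analysis.** C.8.1 compares post-phase outcomes between treatments, adjusting for pre-phase value, phase and sequence. Under C.7.3 the exercise tests are at Visits 1, 6, 7 and 12, so Visit 7 supplies the Period 2 pre-phase value.

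**The concern.** The schedule gives two different weeks for lowering study drug in Period 1. The footnote is part of the treatment schedule that site staff and the pharmacy would work from. If it were followed as written, carvedilol-first subjects would have their Period 1 post-phase peak VO2 measured after carvedilol had been withdrawn. Placebo-first subjects would have their Period 2 value measured before any decrease. The primary contrast would then mix on-drug and off-drug measurements by sequence.

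The second matter is separate and conditional. In a crossover trial the washout protects the start of Period 2. If the visit windows allow it to be shorter than stated, residual carvedilol could affect the Visit 7 test in the carvedilol-first sequence only. It would then enter a covariate of the primary model.

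**Working it through.** **1. The footnote against the cells it annotates**

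- Period 2: week 31 − week 30 = +1 week, after the visit.
- Period 1: week 6 − week 12 = −6 weeks, before the visit.
- The Visit 6 window does not explain the difference. The earliest permitted Visit 6 is 12 − 2 = week 10, still 10 − 6 = 4 weeks after week 6.

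| Place | When drug is lowered or stopped in Period 1 |
|---|---|
| Table 5 footnote | week 6 |
| Table 5, Visit 6 cell | after the week-12 visit |
| C.5.3.2 with Table 5 | in the washout, weeks 13–18 |
| Overview | after a 12-week first period |
| C.7.2 | no timing given, but the Visit 6 test is meant to follow time to reach the maximum tolerated dose |

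The footnote disagrees with each of the others.

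**2. The stated washout, reproduced**

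Weeks 13 to 18 counted inclusively: 18 − 13 + 1 = 6 weeks = 42 days. This agrees with the Overview.

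**3. What the windows permit between Visit 6 and Visit 7**

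Two points are open: how a week number becomes a day, and what Visit 7 is timed from. All gaps below include the taper, which C.5.3.2 places inside the washout.

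*Convention A, week n = day 7n.* Visit 6 is day 84 and Visit 7 is day 19 × 7 = 133.

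- Nominal gap: 133 − 84 = 49 days.
- Both visits timed from randomization: shortest (133 − 7) − (84 + 14) = 126 − 98 = 28 days; longest (133 + 7) − (84 − 14) = 140 − 70 = 70 days. With Visit 6 on time, the shortest is 126 − 84 = 42 days, so a gap under 42 days needs a late Visit 6.
- Visit 7 timed from the actual Visit 6: 49 ± 7 = 42 to 56 days.

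*Convention B, weeks counted inclusively.* Visit 6 is at the end of week 12 (day 84) and Visit 7 at the start of week 19, day 18 × 7 = 126.

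- Nominal gap: 126 − 84 = 42 days.
- Both visits timed from randomization: shortest (126 − 7) − 98 = 21 days; longest (126 + 7) − 70 = 63 days. With Visit 6 on time, the shortest is 119 − 84 = 35 days.
- Visit 7 timed from the actual Visit 6: 42 ± 7 = 35 to 49 days.

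| Convention | Nominal | From randomization | From actual Visit 6 |
|---|---|---|---|
| A (week n = day 7n) | 49 | 28–70 | 42–56 |
| B (inclusive weeks) | 42 | 21–63 | 35–49 |

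**4. Which convention do the documents support?**

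Neither is settled. The Overview's count of the tests from randomization, and Visit 1 at week 0, favour A. But under A, Visit 7 to Visit 12 is (30 − 19) × 7 = 77 days, or 11 weeks, against the stated 12. Under B it is 210 − 126 = 84 days, or 12 weeks, and the washout is exactly 6 weeks.

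**5. The completion visit**

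C.5.6 defines completion by an assessment at 31 ± 2 weeks, and Table 5 has no visit at week 31. The Visit 12 window of 30 ± 2 weeks plus a one-week taper gives 31 ± 2 weeks, so the figure is largely explained. Only a label is missing.

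**The case against.** **On the footnote.** Everything else in the schedule points away from week 6. Table 5 has no week-6 visit: Visit 4 is at week 3, and Visit 5, at week 8, may be by phone. C.5.3.4 dispenses drug at Visits 1–4 and 7–10, so no dispensing event falls at week 6. Compliance checks continue at weeks 8 and 12, which presupposes that drug is being taken. The annotated visit is number 6, so a visit number written for a week number is a natural explanation. This stands, and it limits what can be claimed. A reader might infer that Period 1 subjects will be off drug for weeks before their primary-outcome test and count the days. The documents do not support that inference, because the annotated cell and C.5.3.2 both exclude it. What remains is a contradiction in a treatment instruction.

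**On the washout.** The planned schedule meets 6 weeks, no section calls 6 weeks a minimum, and no section fixes the reference date for the windows. The model already adjusts for the Visit 7 value, phase and sequence. All of this is fair. Two stronger readings should be avoided. One is that the windows definitely breach the washout: timed from the actual Visit 6 under convention A, the gap is at least 42 days. The opposite is that an on-time Visit 6, or timing from the actual Visit 6, always protects the 42 days: under convention B each can give 35. Nor should a count of permitted day pairs be read as a risk, since the documents say nothing about how visits will fall within their windows.

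**On completion.** A reader might infer that trial completion is undefined. The one-week taper after Visit 12 largely accounts for week 31.

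**Conclusion.** The footnote contradiction holds with high confidence and rests on no assumption. Week 6 is six weeks before the cell it annotates and conflicts with C.5.3.2, the Overview and the purpose stated in C.7.2. It is probably a slip, but the documents do not say so. It should be corrected because a literal reading would affect the Period 1 primary-outcome test and not the Period 2 test.

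The washout point is secondary, conditional and held with lower confidence. The shortest permitted gap is 21, 28, 35 or 42 days, depending on an unstated reference date and an unstated way of counting weeks. Three of these four readings allow less than the stated 42 days. Any residual drug effect at Visit 7 would arise only in the carvedilol-first sequence, and its size cannot be computed from the documents.

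The week-31 assessment is a note only. No sample size, power or alpha figure changes.

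**What to change.** 1. The sponsor should reconcile the Table 5 footnote with the Visit 6 and Visit 12 cells, C.5.3.2 and the Overview, and state which timing is intended. This costs a wording correction.
2. In C.7.2, state what the Visit 6 and Visit 7 windows are measured from, how Table 5 weeks convert to days, and whether the 6-week washout is a minimum. Then reconcile the windows and the stated washout with each other. This costs wording, a visit calculator, and possibly slightly longer participation for subjects with a late Visit 6.
3. As a note, label the assessment that C.5.6 means by 31 ± 2 weeks.

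No taper timing, washout length or dosing rule is proposed; those choices are the sponsor's.
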